### **4.3. EOS Analysis**

The EOS analysis includes all data obtained until 6 months post-last dose.

This SAP is focused / limited to planned first and EOS analyses. Outputs required for the first analyses will be flagged in the tables, figures and listings (TFL) mock shells document.

CCI

## 5. ANALYSIS SETS

Agreement and authorization of participants included / excluded from each analysis set will be conducted prior to production for the first analysis.

### 5.1. Process for Analysis Set Assignment

- Definitions for analysis sets are provided below.
- Prior to database lock, a transfer of raw data from the electronic Case Report Form (eCRF) will occur, and participants will be assigned to analysis sets in accordance with the definitions in this SAP and the available data at that time. However, the protocol deviations will be monitored continuously throughout the study.
- Listings presenting participants excluded from each final analysis set and reasons for exclusion will be prepared for sponsor review ahead of database lock in order to allow appropriate related data queries to be issued.
- A Data Review meeting will be held to confirm analysis set assignment, along with protocol deviations review (see protocol deviations management plan [PDMP], to include details of which PDs lead to exclusion from per protocol analyses), for each participant and any changes will be recorded. Changes will be implemented, and an updated analysis set assignment will be approved by the sponsor.
- Sponsor authorization of the analysis sets will be necessary prior to database lock. Once approved, analysis sets will be finalized, and the database will be locked.
- After database lock, the final analysis sets will be derived using the final study data, i.e., clinical database (eCRF), eDiary, external vendor data (immunogenicity results) and protocol deviations log.

[figure not shown]
### 5.2. Screened Set [SCR]

All participants who were screened for eligibility.

### 5.3. Enrolled Set [ENR]

All participants in the SCR who entered the study who were randomized or received study intervention or underwent a post-screening study procedure. For analyses and displays based on ENR, participants will be classified according to randomized intervention.

CCI

## 5.4. Exposed Set [ES]

All participants in the ENR who received at least one study intervention. Analysis per group is based on the study intervention administered (i.e., study intervention actually received).

## 5.5. Per Protocol Set [PPS]

### RSV PPS:

All eligible participants in the ES:

- who received RSV vaccine as per protocol in the control group and received all the study interventions in the Co-Ad group
- who had immunogenicity results pre- and post-dose for RSV neutralizing titers
- who complied with blood draw interval for RSV samples
- without intercurrent medical conditions that may interfere with immunogenicity and without prohibited concomitant medication/vaccination\* up to blood sample post RSV vaccination for control group and blood sample post HZ/su vaccine dose 2 vaccination for Co-Ad group, and
- who do not meet any of the criteria for elimination up to blood sample post RSV vaccination for control group and blood sample post HZ/su vaccine dose 2 vaccination for Co-Ad group (i.e., control group subjects need to meet all above criteria at Visits 2 and 3; Co-Ad group subjects need to meet all above criteria at Visits 1, 2, 3 and 4).

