**Table 17 Analysis Sets**

Analysis Set	Description
Screened set	All participants who were screened for eligibility
Enrolled set 	All participants who entered the study who were randomized or received study intervention or underwent a post-screening study procedure.
Exposed set	All participants who received at least one study intervention. Analysis per group is based on the study intervention administered.
RSV PPS 	All eligible participants: 
 
Who received RSV vaccine as per-protocol in the control group and received all the study interventions in the Co-ad group
 
Who had immunogenicity results pre and post-dose for RSV neutralizing titers
 
Who comply with the blood draw intervals for RSV samples
 
Without intercurrent medical conditions that may interfere with immunogenicity and without prohibited concomitant medication/vaccination up to blood sample post RSV vaccination for control group and blood sample post HZ/su vaccine dose 2 vaccination for Co-ad group
 
Who do not meet any of the criteria for elimination up to blood sample post RSV vaccination for control group and blood sample post HZ/su vaccine dose 2 vaccination for Co-ad group
 

HZ/su PPS 	All eligible participants: 
 
Who received two doses of HZ/su vaccine as per-protocol in the control group and all study interventions in the Co-ad group
 
Who had immunogenicity results pre and post-dose for anti-gE antibody concentrations
 
Who comply with the blood draw intervals for zoster samples
 
Without intercurrent medical conditions that may interfere with immunogenicity and without prohibited concomitant medication/vaccination up to blood sample post HZ/su vaccine dose 2 vaccination
 
Who do not meet any of the criteria for elimination up to blood sample post HZ/su vaccine dose 2 vaccination
 

Abbreviations: C-ad=co-administration group; HZ/su=herpes zoster/subunit; PPS=per protocol set;

RSV=respiratory syncytial virus.

 Screen failures (who never passed screening even if rescreened) and participants screened but never enrolled into the study (met eligibility but not needed to reach the target enrollment) are excluded from the Enrolled Set as they did not enter the study

 Contribution of participants to PPS will be defined by timepoint

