Primary	RSVPreF3 OA (one dose) and HZ/su (two doses) co-administered (Co-Ad) or received separately (Control)	Adults aged $\geq$ 50 YOA	GMTs for RSV-A neutralizing titers	
1. Permanently discontinued from study due to any reasons prior to 30 days after vaccine administration (Visit 4 for Co-Ad group and Visit 3 for Control group)
 
2. Study intervention not administered per protocol
 
3. Prohibited medication or intercurrent medical condition prior to 30 days after vaccine administration (Visit 4 for Co-Ad and Visit 3 for Control group)
 
4. RSVPreF3 OA investigational vaccine or
	
1. Missing data won't be imputed. Summaries will present the actual data.
 
2. Participant excluded from the immunogenicity analysis.
 
3. Participant excluded from the immunogenicity analysis.
 
4. Participant excluded from the immunogenicity analysis.
 
5. Participant excluded from the immunogenicity analysis.
	The least square point estimate and its 2-sided 95% CI for between group GMT ratio derived from an ANCOVA model which includes the treatment group and the age category (age at vaccination: 50 to 59, 60 to 69, or $\geq$ 70) as fixed effects, and the pre-vaccination log10 transformed titer as covariate, in terms of RSV-A neutralizing titers between Control group over Co-Ad group at 1-month after the RSVPreF3 OA investigational vaccine dose (i.e., at Day 31 for Co-Ad group, and at Day 61 for Control group).

				
blood sample for RSV neutralizing titers (for baseline or testing) taken out of window
 
5. No pre / post-vaccine immunogenicity results for RSV-A neutralizing titers available
		

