### HZ/su PPS:

All eligible participants in the ES:

- who received two doses of HZ/su vaccine as per protocol in the control group and received all the study interventions in the Co-Ad group
- who had immunogenicity results pre- and post-dose for anti-gE antibody concentrations
- who complied with blood draw interval for zoster samples
- without intercurrent medical conditions that may interfere with immunogenicity and without prohibited concomitant medication/vaccination\* up to blood sample post HZ/su vaccine dose 2 vaccination, and
- did not meet any of the criteria for elimination up to blood sample post HZ/su vaccine dose 2 vaccination (i.e., control group subjects need to meet all above criteria at Visits 1, 3 and 4; Co-Ad group subjects need

to meet all above criteria at Visits 1, 2, 3 and 4).

\*Intercurrent medical conditions that may lead to elimination from the PPS are defined as confirmed immunodeficiency condition.

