**Table E: Window convention (Co-Ad Group and Control Group)**

Assigned Study Day	Visit label as per protocol	Visit assigned
Day 1	Visit 1	Visit 1 (Day 1)
Day 31 (Day 1 + 30 to 42 days)	Visit 2	Visit 2 (Day 31)
Day 61 (Day 1 + 60 to 84 days)	Visit 3	Visit 3 (Day 61)
Day 91 (Day 1 + 90 to 126 days)	Visit 4	Visit 4 (Day 91)

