## 15. IMMUNOGENICITY OUTCOMES

The primary analysis will be based on the applicable PPS (i.e., RSV PPS or HZ/su PPS) for analysis of immunogenicity. If, in any study intervention group, the percentage of vaccinated participants with serological results excluded from the applicable PPS for analysis of immunogenicity is 5% or more, a second analysis based on the ES will be performed to complement the PPS analysis.

CCI

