### 15.1.3. Primary Analysis of Primary Immunogenicity Variables

The primary immunogenicity endpoints will be analyzed as follows:

- Between groups GMC ratio for HZ/su vaccine between the Control group over Co-Ad group for gE Ab concentrations (IU/mL) at 1-month after the second HZ/su vaccination (i.e., at Day 91 for both Co-Ad and Control groups) and 2-sided 95% CI will be computed.
  - The least square point estimate and its 95% 2-sided CIs of the between group GMC ratio will be derived from an ANCOVA model on log10 transformed concentrations and presented alongside descriptive GMCs and 95% CIs. The ANCOVA model will include the treatment group and age category (age at vaccination: 50 to 69, 60 to 69, or  $\geq 70$  YOA) as fixed effects, and the pre-vaccination log10-transformed concentration as covariate. The results will be presented in tables as well as graphs using forest plots.
- Between group GMT ratio for RSV investigational vaccine between the Control group over Co-Ad group

CCI

for RSV-A neutralizing titers (ED60) at 1-month after the RSVPreF3 OA investigational vaccine dose (i.e., at Day 31 for Co-Ad group, and at Day 61 for Control group) and 2-sided 95% CI will be computed.

- The least square point estimate and its 95% 2-sided CIs will be derived from an ANCOVA model on log10 transformed titers and presented alongside descriptive GMTs and 95% CIs. The same ANCOVA model used for the HZ/su GMC ratio will be applied for this summary. The results will be presented in tables as well as graphs using forest plots.
- Between group GMT ratio for RSV investigational vaccine between the Control group over Co-Ad group for RSV-B neutralizing titers (ED60) at 1-month after the RSVPreF3 OA investigational vaccine dose (i.e., at Day 31 for Co-Ad group, and at Day 61 for Control group) and 2-sided 95% CI will be computed.
  - The least square point estimate and its 95% 2-sided CIs will be derived from an ANCOVA model on log10 transformed titers and presented alongside descriptive GMTs and 95% CIs. The same ANCOVA model used for the HZ/su GMC ratio will be applied for this summary. The results will be presented in tables as well as graphs using forest plots.

A successful primary immunogenicity conclusion will require:

First sequence:

- The upper limit of the 2 sided 95% CI of the GMC ratio between the Control group (at Day 91) versus Co-ad group (at Day 91) for anti-gE Ab 1-month after the second HZ/su vaccine dose is  $\leq 1.5$ .

AND

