#### **15.1.4. Analysis for Primary Immunogenicity Variables**

Sensitivity analysis will be performed on the primary immunogenicity endpoints using the same primary ANCOVA model with the treatment group and age category (age at vaccination: 50-59, 60-69 or  $\geq 70$  years) as fixed effects and the pre-vaccination log10-transformed concentration or titer as applicable, as regressors, and with the addition of center as a random effect.

A second sensitivity analysis for the primary immunogenicity endpoints for RSV-A/B will be performed as described in Section 15.1.3. on a modified PPS including participants who received only one dose of HZ/su vaccine in the Co-Ad group.

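### The RSV per-protocol set drops Co-Ad participants, but not Control participants, for events that occur after their RSV endpoint sample

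*SAP*

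**What the plan says.** **Endpoint.** SAP 15.1.3 takes the RSV-A and RSV-B titers "at Day 31 for Co-Ad group, and at Day 61 for Control group". These are Visit 2 and Visit 3, each one month after that group's RSV dose. Protocol 9.3.1 bases the confirmatory analyses on the per-protocol set (PPS).

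**RSV PPS.** SAP 5.5 and Protocol Table 17 use different rules by arm. Control participants need the RSV vaccine per protocol and must meet the criteria up to the post-RSV sample, which the SAP spells out as Visits 2 and 3. Co-Ad participants need every study intervention, which includes HZ/su dose 2 at Visit 3, and must meet the criteria up to the sample after that dose: "Co-Ad group subjects need to meet all above criteria at Visits 1, 2, 3 and 4". Under the Protocol's schedule of activities, the Co-Ad Visit 4 sample serves the HZ/su testing, not the RSV testing.

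**What can exclude.** Prohibited medication or vaccination, the elimination criteria, and intercurrent conditions. On the last, the SAP says "Intercurrent medical conditions that may lead to elimination from the PPS are defined as confirmed immunodeficiency condition".

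**Statements that do not fit together.** Footnote [2] of Protocol Table 17 says "Contribution of participants to PPS will be defined by timepoint". In SAP 2.4, the third intercurrent event in the RSV-A primary row, handled by exclusion, is "Prohibited medication or intercurrent medical condition prior to 30 days after vaccine administration (Visit 4 for Co-Ad and Visit 3 for Control group"). The RSV-B primary row has the same cut-offs.

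**Supporting analyses.** SAP 15.1.4 repeats the RSV analysis "on a modified PPS including participants who received only one dose of HZ/su vaccine in the Co-Ad group". SAP 15 adds that, if 5% or more of vaccinated participants with serological results in any group are excluded from the applicable PPS, "a second analysis based on the ES will be performed to complement the PPS analysis".

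**The concern.** A per-protocol set for a given endpoint should depend on what happened up to that endpoint. Here it does so for Control but not for Co-Ad. Suppose a participant in each arm has a valid post-RSV titer and then misses HZ/su dose 2 or takes a prohibited product. The Control participant stays in the RSV test; the Co-Ad participant can be removed from it.

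The extra condition does not serve the RSV objective, which concerns the RSV vaccine given with the first HZ/su dose. Dose 2 comes after the Co-Ad RSV sample. Nor need the later exclusions be random. Through Protocol 9.2.1 and 7.1.1 they can include related serious adverse events, anaphylaxis, new or worsened immune-mediated disease and immune-modifying treatment, any of which could be associated with immune response.

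The PPS result alone decides RSV-A (co-primary) and RSV-B (sequential). If the removed Co-Ad participants tended to have low titers, the Co-Ad mean would be raised and non-inferiority would be too easy to show. If they tended to have high titers, it would be too hard.

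**Working it through.** **1. Timing.** SAP Table C allows 30 to 42 days from Visit 1 to Visit 2, 60 to 84 from Visit 1 to Visit 3, and 30 to 42 from Visit 3 to Visit 4. Visit 4 therefore falls 60 + 30 = 90 to 84 + 42 = 126 days after Day 1, which agrees with SAP Table E: "Day 91 (Day 1 + 90 to 126 days". From the Co-Ad RSV sample (Visit 2) to the end of the Co-Ad criteria (Visit 4):

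- planned: 90 − 30 = 60 days
- shortest: 90 − 42 = 48 days
- longest: 126 − 30 = 96 days

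For Control, the gap between the RSV sample and the end of the criteria is zero.

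**2. The estimand wording.** In Co-Ad the RSV dose is given on Day 1, so 30 days after it is Visit 2. The RSV rows name Visit 4. For Control, the RSV dose is at Visit 2 and 30 days later is Visit 3, as the rows say. Only the Co-Ad visit is out of step with the rule beside it.

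**3. The plan's own power.** Inputs from Protocol Table 19: SD 0.45 on log10, 225 per arm, true ratio 1.05, margin 1.5, one-sided alpha 2.5%.

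- SE = 0.45 × √(2/225) = 0.0424
- (log10 1.5 − log10 1.05)/SE = (0.176 − 0.021)/0.0424 ≈ 3.65
- Power by the noncentral t (448 df) = 95.4%, as stated

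This figure is not affected, because 225 per arm is already net of PPS exclusions (Protocol 9.5).

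**4. Illustration of bias.** Let f be the fraction of otherwise evaluable Co-Ad participants removed only for reasons arising after Day 31. Let d be the amount, in log10, by which their mean titer lies below that of the Co-Ad participants kept. Neither is in the documents; both are assumptions.

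- Co-Ad mean overstated by f × d
- Control/Co-Ad ratio understated by the factor 10^(f × d)
- One-sided type I error at a true ratio of 1.5 = Φ(−1.96 + f × d/SE)

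| f | d | f × d | Factor | Type I error |
|---|---|---|---|---|
| any | 0 | 0 | 1.000 | 2.5% |
| 3% | 0.1 | 0.003 | 1.007 | 2.9% |
| 5% | 0.2 | 0.010 | 1.023 | 4.2% |
| 4.9% | 0.3 | 0.0147 | 1.034 | 5.3% |
| 5% | −0.2 | −0.010 | 0.977 | 1.4% |

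Worked for the third row: −1.96 + 0.010/0.0424 = −1.72, and Φ(−1.72) ≈ 4.2%. The shift of 0.010 is under 6% of the 0.176 margin. With 225 kept, 5% removed is 225/0.95 × 0.05 ≈ 12 participants. A simulation of 200,000 t-tests per row agrees with the formula to within about 0.1 percentage points.

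**The case against.** The strongest case against has five parts.

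- **The inputs are not in the plan.** Nothing supports a 0.2 log10 deficit (titers about 37% lower, since 10^−0.2 = 0.63) among those removed; zero is as defensible. This stands, and the table should be read as illustration, not as an estimate.
- **The SAP has safeguards.** The second sensitivity analysis restores Co-Ad participants who had only one HZ/su dose, so that part of the problem was foreseen. It does not restore those who received dose 2 and were removed for medication, vaccination or another elimination criterion between Visits 2 and 4. The Exposed Set analysis keeps the Day 31 titers and would run at f = 5%. The 4.9% row escapes it only if almost no one else with serological results is excluded. Both analyses are supportive; neither decides success.
- **The test is an ANCOVA.** It adjusts for pre-vaccination titer and age category, so only a deficit that these do not explain causes bias. This stands: d must be read as that residual deficit. Adjustment would also reduce the SE, so the net effect on the table is unknown.
- **The text is ambiguous rather than wrong.** Footnote [2] could let Day 31 data count whatever happens later, discontinuation in SAP 2.4 is handled by presenting actual data, and Protocol 9.2.1 says only that participants may be eliminated. But the visit list in SAP 5.5 is explicit, and the third intercurrent event excludes through Visit 4.
- **The arms are already unequal.** Control must stay in the study to Day 61 to have an RSV endpoint, Co-Ad only to Day 31. That is true and comes from the design. It does not justify adding selection after the endpoint in Co-Ad.

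**Conclusion.** The concern holds. As written, the confirmatory RSV-A and RSV-B tests can discard valid Co-Ad titers because of events 48 to 96 days' worth of follow-up beyond the endpoint sample, with no equivalent rule in Control. That follows from the text and needs no assumption.

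The consequence is less certain. Direction and size depend on how many are removed and on whether their titers differ after adjustment, and the documents give neither. Over the cases shown, type I error runs from 1.4% to 5.3% against the planned 2.5%, and the ratio shifts by at most a factor of 1.034. If removal is unrelated to titer there is no bias. The effect is probably small, but it bears on a primary conclusion, the extra condition adds nothing to the RSV question, and the correction is cheap. It should be fixed.

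**What to change.** - **SAP 5.5 and Protocol Table 17:** define the RSV PPS up to the one-month post-RSV sample in both groups: Visit 2 for Co-Ad and Visit 3 for Control. For the RSV endpoints, drop the requirement for HZ/su dose 2 and the Visit 3 and Visit 4 criteria in Co-Ad. This also brings Table 17 into line with its footnote [2].
- **SAP 2.4:** in the RSV-A and RSV-B rows, primary and secondary, replace Visit 4 by Visit 2 for Co-Ad.
- **SAP 15.1.4:** keep the present, stricter RSV set as a sensitivity analysis. The existing one-dose analysis then becomes redundant, because those participants are already in the main set.
- **SAP 3.3:** if the Protocol table is not amended, record the change here, where the SAP now reports none.

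The cost is wording and a revised analysis-set flag; no new data, visits or participants are needed. The change removes the post-endpoint selection only. The 30-day wait before the RSV dose in Control is part of the design and remains.

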### HZ/su PPS:

All eligible participants in the ES:

- who received two doses of HZ/su vaccine as per protocol in the control group and received all the study interventions in the Co-Ad group
- who had immunogenicity results pre- and post-dose for anti-gE antibody concentrations
- who complied with blood draw interval for zoster samples
- without intercurrent medical conditions that may interfere with immunogenicity and without prohibited concomitant medication/vaccination\* up to blood sample post HZ/su vaccine dose 2 vaccination, and
- did not meet any of the criteria for elimination up to blood sample post HZ/su vaccine dose 2 vaccination (i.e., control group subjects need to meet all above criteria at Visits 1, 3 and 4; Co-Ad group subjects need

to meet all above criteria at Visits 1, 2, 3 and 4).

\*Intercurrent medical conditions that may lead to elimination from the PPS are defined as confirmed immunodeficiency condition.

## 6. GENERAL CONSIDERATIONS

Data will be summarized descriptively.

For categorical data: N, percentage.

For continuous data: N, mean, SD, median, maximum, minimum.

In summary tables for categorical data for which categories are defined on the eCRF, all categories will be presented as specified, even if the participants count within that category is zero.

Unless otherwise specified, all data collected during the trial will be presented in listings for the SCR.

### 6.1. Reference Start Date and Study Day

Study Day will be calculated from the reference start date and will be used to show start / stop day of assessments and events. It will appear in every listing where an assessment date or event date appears.

Reference start date is defined as the day of the first dose of each study vaccination, which is Day 1 for all participants.

If the date of the event is on or after the reference date, then:

[figure not shown]
- Study Day = (date of event – reference date) + 1.

If the date of the event is prior to the reference date, then:

- Study Day = (date of event – reference date).

In the situation where the event date is partial or missing, Study Day, and any corresponding durations will appear partial or missing in the listings unless otherwise stated.

CCI

## **6.2. Baseline**

Unless otherwise specified, baseline is defined as the last non-missing measurement taken prior to reference start date (including unscheduled assessments) and will be referenced as pre-vaccination. If time is not collected, Day 1 assessments are assumed to be taken prior to first dose and used as baseline.

## **6.3. Retests, Unscheduled Visits and Early Termination Data**

[figure not shown]
In general, for by-visit summaries, data recorded at the nominal visit will be presented.

Listings will include scheduled, unscheduled, retest and early discontinuation data.

